5.6.6 Other Safety Analyses

Other safety analyses will include the following:

- Change in puberty status
- Waist circumference
- DEXA Z-score
- Cognition
- Depression
- Valvular function
- Pulmonary pressures

6 INTERIM ANALYSES

"No interim analyses are planned for this study."

7 CHANGES IN THE PLANNED ANALYSES

Due to the early termination of the study, the following changes are made from the initial planning for the study:

1. There will be no ANCOVA or MMRM analysis for any of the efficacy endpoints. Only basic summary of descriptive statistics will be presented.
2. All secondary endpoint analysis of type 2 diabetes will not be provided since there is only 1 subject of type 2 diabetes.
3. All planned supportive and sensitivity analysis (MMRM, MNAR imputation, per protocol) will not be performed.
4. Summary of major protocol deviation will not be performed and only data listing will be presented.
5. No subgroup analysis will be performed for the primary endpoint analysis.

8 HANDLING OF MISSING DATA, DROP-OUTS, AND OUTLIERS

For determining treatment emergent markedly abnormal lab values, a missing baseline lab value will be assumed to be of grade 0.

No special handling of missing data is planned for the analysis of any of the efficacy or safety variables.

8.1.1 Visit Windowing

Table 1 will be applied to all measurements including those from unscheduled visits and early termination visits to attain the measurement for analysis for the given scheduled visit.

Table 1 Windowing Rules for Safety Endpoints

Visit	Target Visit Day (in study days)	Visit Window (in study days)
Week 0	Day 1	Day 1
Week 1	7	2-21
Week 5	35	22-45
Week 8	56	46-70
Week 12	84	71-112
Week 20	140	113-168
Week 28	196	169-224
Week 36	252	225-280
Week 44	308	281-336
Week 52	364	337-379
Week56/FU		>379 or analysis visit date > last dose date +14
EOT		For last non missing analysis visit date ≤≤ 379 or ≤≤ last dose date +14 days.

In case of multiple assessments within the same visit window, the assessment closest to the target visit day will be used in data analyses; in the event of two assessments being equally close to the scheduled visit day, the latest assessment in the sequence will be used.

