3.1 Study Objectives

3.1.1 Primary Objective

- To demonstrate weight loss efficacy by change in body mass index (BMI) during 52 weeks of treatment with Belviq XR 20 mg administered QD as compared to placebo

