3.2 Overall Study Design

This is a multicenter, randomized, double-blind, placebo-controlled, parallel-group study in obese adolescents ages 12 to 17 years. Approximately 260 subjects will be randomized in a 1:1 ratio to Belviq XR 20 mg QD (130 subjects) and placebo (130 subjects). Subjects will be stratified by sex. Subjects will receive Belviq XR 20 mg or matched placebo QD in a 1:1 ratio for up to 52 weeks. A recruitment plan will be developed to ensure at least 20% of younger subjects (12 to 13 years of age) are enrolled in the study.

Throughout the duration of the study, subjects will be encouraged to adhere to a lifestyle modification program that includes a standardized, age-appropriate diet and exercise counseling (see [Appendix 2](#)).

The study will consist of 2 phases: Prerandomization and Randomization. The Prerandomization Phase will last up to 30 days and consists of 1 visit during which subjects will be screened for eligibility. The Randomization Phase consists of a Treatment Period and a Follow-Up Period. The Treatment Period will last for a maximum of 52 weeks, with visits at Weeks 1, 5, 8, 12, 20, 28, 36, 44, and 52; the Follow-Up Period will extend from the End of Treatment (EOT) visit to the End of Study (EOS) visit.

Subjects who screen fail can be rescreened only once. All subjects will continue in the study until the 52-week evaluation is completed. Subjects who discontinue treatment prematurely will be followed up until study completion. All attempts will be made to capture height and weight in all subjects whether or not they are still on study drug at the end of the study.

Details of the study procedures and schedule of assessments can be found in Table 2 of the protocol.

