5.3.5 Handling of Missing Data, Dropouts, and Outliers

Due to the early termination of the study, no imputation analysis will be performed.

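### Table 1 can move off-drug BMI values out of Week 52: its last-dose clause has no stated precedence over the study-day windows and is applied to all measurements

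*SAP*

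**What the plan says.** - **Scope of the windows.** Section 8.1.1 states that "Table 1 will be applied to all measurements including those from unscheduled visits and early termination visits". The caption of the same table reads "Windowing Rules for Safety Endpoints". The SAP contains no other windowing rule for BMI.
- **Week 52 row.** Target Day 364, window Days 337 to 379.
- **Follow-Up row.** ">379 or analysis visit date > last dose date +14".
- **Design.** Section 3.2: "Subjects who discontinue treatment prematurely will be followed up until study completion", and "All attempts will be made to capture height and weight in all subjects whether or not they are still on study drug".
- **Population.** Sections 5.2.1 and 5.4 base efficacy on the FAS, meaning everyone randomised who took at least one dose.
- **Missing values.** Section 5.3.5: "Due to the early termination of the study, no imputation analysis will be performed". Section 8 adds no other handling for efficacy variables.
- **What is still reported.** Sections 5.4.1 to 5.4.3 keep descriptive summaries of Week 52 BMI change, the 5% and 10% responder rates at Week 52, the 5% responder rate at Week 12, and Week 52 results split by Week 12 response.

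**The concern.** The design keeps people who stop drug in the study and tries to weigh them at the end, so an FAS summary of Week 52 BMI would be expected to include those weights. The Follow-Up row can relabel the same weights because the last dose was more than 14 days earlier. Nothing is imputed, so a relabelled value would simply be absent from Week 52. The table would still be labelled FAS but would describe mainly subjects on drug, or within 14 days of their last dose, at Week 52. Section 7 lists the changes made because of early termination, and this restriction is not among them. Early termination explains why many subjects have no Week 52 weight. It gives no reason to relabel a weight that was taken on Day 364.

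The text also leaves the content of the primary endpoint to the programmer. Two people working from section 8.1.1 could put the same BMI value under different visits.

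**Working it through.** The plan states no figure for this point, so the check is of the table's logic. Inputs are the Table 1 windows and the 14-day clause. Let V be the study day of the visit and L the study day of the last dose.

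**Step 1: do the scheduled windows leave gaps?** The windows are Day 1, 2–21, 22–45, 46–70, 71–112, 113–168, 169–224, 225–280, 281–336 and 337–379. Their lengths are 1 + 20 + 24 + 25 + 42 + 56 + 56 + 56 + 56 + 43 = 379 days. Each day from 1 to 379 falls in exactly one window, and the first half of the Follow-Up rule takes every later day. The last-dose half therefore never fills a gap. For any V ≤ 379 it either overrides a scheduled window or puts a second label on the same value.

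**Step 2: which Week 52 days meet the Follow-Up rule?** The condition is V > L + 14.

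| Last dose (L) | Days in 337–379 that also meet Follow-Up | Count of 43 |
|---|---|---|
| 322 or earlier | 337–379 | 43 |
| 336 | 351–379 | 29 |
| 350 | 365–379 | 15 |
| 364 | 379 | 1 |
| 365 or later | none | 0 |

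- A visit on the target day, V = 364, escapes Follow-Up only if L ≥ 364 − 14 = 350.
- A visit on the first day of the window, V = 337, escapes only if L ≥ 337 − 14 = 323. With L ≤ 322 the whole window is claimed.

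**Step 3: the same at Week 12** (target Day 84, window 71–112). A Day 84 visit escapes only if L ≥ 84 − 14 = 70. The whole window is claimed if L ≤ 71 − 15 = 56.

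**Step 4: one subject through the table.** Take L = 140 and a last visit at V = 364.

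- Week 52 row: 337 ≤ 364 ≤ 379, met.
- Follow-Up row: 364 > 140 + 14 = 154, met.
- End-of-treatment row: its two conditions are joined by an or, and 364 ≤ 379, so it is met too.

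Three rows claim one value. The only tie-break in section 8.1.1 chooses between several assessments in one window. It does not choose between several rows for one assessment, and the Follow-Up row has no target day to measure closeness against.

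**The case against.** The strongest reply is that the override is not written down. The end-of-treatment row picks a last value that will usually sit in a scheduled window as well, so Table 1 rows can overlap. The Follow-Up label could be a second label of the same kind, serving the shift tables in section 5.6.3 that use End of Treatment and Follow-Up. A stopper's Day 364 BMI would then remain at Week 52. The caption limits the table to safety, and section 9 leaves derivation rules to documents not seen here. Section 3.2 promises to collect off-drug weights without saying that they enter the Week 52 summary, and the primary objective is framed as "To demonstrate weight loss efficacy by change in body mass index (BMI) during 52 weeks of treatment with Belviq XR 20 mg".

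Much of this stands. The exclusion is the likeliest reading, not a stated rule, and a reader should not report it as one. Override remains likelier because double labelling would count one measurement under both Week 52 and Follow-Up in by-visit summaries. The caption does not settle the matter, since the sentence above it says the opposite and BMI has no other rule. Under either reading the section does not fix which BMI values form the primary endpoint.

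The decision not to impute is disclosed in section 5.3.5, and section 7 lists the dropped sensitivity analyses. It is not an error, and an added table counting withdrawals as non-responders would be a debatable preference.

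**Conclusion.** The point holds as a badly fixed rule with a likely unintended consequence. If the last-dose clause takes precedence, measured off-drug BMI values leave the Week 52 and Week 12 FAS summaries, at odds with the follow-up in section 3.2 and undeclared in section 7. If it does not, the text still needs to say so.

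The size is unknown. Only subjects who stopped drug and were later weighed inside a scheduled window, more than 14 days after their last dose, are affected, and the SAP does not count them. Section 3 says about 20% of subjects completed Week 52, so many missing Week 52 values may come from termination, not from windowing. Results are descriptive only.

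Three stronger inferences are tempting and unsupported:

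- **Sizing the effect from the 40% dropout in section 4.** That calculation treats dropouts as having no Week 52 data. With 130 × 0.6 = 78 per arm, power is 80.5% for the t-test and 78.4% for the chi-square test, matching the stated figures of at least 80% and above 78%. Subjects without a weight have none to relabel.
- **Saying the bias favours the drug.** The direction depends on who stops in each arm. If placebo subjects stop for lack of weight loss, the remaining placebo group looks better and the bias runs the other way.
- **Saying Week 52 is the only efficacy result.** Week 12 response is summarised too.

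**What to change.** In section 8.1.1:

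1. State that weight, height and BMI used for efficacy are assigned to scheduled visits by study day alone, whatever the date of last dose.
2. Limit the last-dose-plus-14-days clause to safety summaries.
3. Reconcile the caption with the sentence that applies the table to all measurements.

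The cost is a sentence or two and matching programming, with no new data. The downside is that Week 52 summaries will mix on-drug and off-drug values and may look less favourable.

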5.6.3 Laboratory Values

Laboratory results will be summarized using standard international units, as appropriate. For all quantitative parameters, the actual value and the change from baseline to each post baseline visit and to the end of treatment (defined as the last on-treatment value) will be

summarized by visit and treatment group using descriptive statistics. Percentages will be based on the number of subjects with both no missing baseline and relevant post baseline results.

Laboratory test results will be assigned a low/normal/high (LNH) classification according to whether the value was below (L), within (N), or above (H) the laboratory parameter's reference range. Within-treatment comparisons for each laboratory parameter will be based on 3-by-3 tables (shift tables) that compare the baseline LNH classification to the LNH classification at the End of Treatment and the Follow-Up visits. Similar shift tables will also compare the baseline LNH classification to the LNH classification for the highest and lowest value during the treatment period.

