5.6.5 Electrocardiograms

For each ECG parameter (including PR interval, RR interval, QRS interval, QT interval, QTc interval (Bazett formula), QTc interval (Fridericia formula), the actual value and change from baseline will be summarized by visit and treatment group using descriptive statistics.

Shift tables will present changes from baseline in ECG interpretation (categorized as normal; abnormal, not clinically significant; and abnormal, clinically significant) to end of treatment.

Maximum post baseline QTc (Bazett) and QTc (Fridericia) will also be tabulated by treatment group as follows:

- Number (percentage) of subjects with
 - greater than 450 msec,
 - greater than 480 msec, and
 - greater than 500 msec during the treatment, and
- Number (percentage) of subjects with an increment of greater than 30 msec and greater than 60 msec from the baseline visit.

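### The *or* in the EOT row of SAP Table 1 lets a value taken long after the last dose count as end of treatment, against Section 5.6.3

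*SAP*

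**What the plan says.** All the windowing rules stand in SAP Section 8.1.1.

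- **EOT row of Table 1:** "For last non missing analysis visit date ≤≤ 379 or ≤≤ last dose date +14 days". I read the doubled sign as a single ≤; nothing below depends on it.
- **Week56/FU row:** ">379 or analysis visit date > last dose date +14". This row has no target day.
- **Week 52 row:** Days 337 to 379, target Day 364. Like the other scheduled weeks after Day 1, it is set by study day alone, with no on-treatment condition.
- **Scope:** the table's title refers to safety endpoints, but the sentence above it says "Table 1 will be applied to all measurements including those from unscheduled visits and early termination visits".
- **Selection rule:** "In case of multiple assessments within the same visit window, the assessment closest to the target visit day will be used in data analyses". This picks among several assessments in one window. It does not say what happens when one assessment meets several windows.

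The results are used elsewhere. Section 5.6.3 summarises laboratory change to "end of treatment (defined as the last on-treatment value", and its shift tables "compare the baseline LNH classification to the LNH classification at the End of Treatment and the Follow-Up visits". The ECG shift table in Section 5.6.5 runs from baseline to EOT: "abnormal, clinically significant) to end of treatment". Section 3.2 makes off-drug visits part of the design: "Subjects who discontinue treatment prematurely will be followed up until study completion".

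**The concern.** Two limits joined by *or* are satisfied when either one is met, so the looser limit governs. For anyone who stops drug early, the looser limit is Day 379, and the 14-day limit then does nothing. The EOT row therefore stops being an on-treatment rule for exactly the subjects for whom it matters, and it contradicts the definition in Section 5.6.3.

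The row also overlaps the Follow-Up row. One record could then supply both the EOT and the Follow-Up column of a laboratory shift table that is meant to show two different time points. An abnormality present on drug and resolved after stopping could be missing from the EOT column. Inferential efficacy analyses have been dropped (Section 7), so the descriptive safety tables are a main remaining output. Two programmers working from this text could build them differently.

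A second, smaller gap is the overlap between Follow-Up and the scheduled weeks. No precedence is stated, and without a target day the closest-to-target rule cannot choose among several Follow-Up records.

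**Working it through.** The plan gives no figure to reproduce here; the check is of the window logic.

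**Inputs.** Table 1 supplies Day 379, the 14-day allowance and the Week 52 window 337 to 379. The last-dose days are my assumptions, chosen to show the range, because the SAP gives no distribution of last-dose dates.

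**Rules as written.** Let *d* be the study day of a value and *L* the study day of the last dose.

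- EOT: *d* ≤ 379 or *d* ≤ *L* + 14, which is *d* ≤ max(379, *L* + 14). The last such value is taken.
- Follow-Up: *d* > 379 or *d* > *L* + 14, which is *d* > min(379, *L* + 14).
- Both rows are met when min(379, *L* + 14) < *d* ≤ max(379, *L* + 14). The number of such days is |379 − (*L* + 14)| = |365 − *L*|.

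| Last dose, *L* | *L* + 14 | Days meeting both EOT and Follow-Up | Number of days |
|---|---|---|---|
| 84 | 98 | 99 to 379 | 281 |
| 182 | 196 | 197 to 379 | 183 |
| 364 | 378 | 379 only | 1 |
| 365 | 379 | none | 0 |
| 370 | 384 | 380 to 384 | 5 |

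**One record followed through.** Last dose Day 84, value on Day 364:

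- Week 52: 337 ≤ 364 ≤ 379, met.
- Follow-Up: 364 > 98, met.
- EOT: 364 ≤ 379, met. It becomes the EOT value if no later value qualifies.
- Time off drug: 364 − 84 = 280 days, against the 14 days in the row's other limit.

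**A shorter gap.** Assume last dose on Day 150 and a follow-up visit 28 days later, on Day 178. It falls in the Week 28 window (169 to 224), meets Follow-Up (178 > 164) and meets EOT (178 ≤ 379).

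**EOT read with *and*.** The condition becomes *d* ≤ min(379, *L* + 14), which is the exact complement of the Follow-Up row. The overlap is then 0 days for every *L*. For *L* = 84, the Day 364 value is no longer EOT. It still meets both Week 52 and Follow-Up, because the scheduled windows ignore treatment status. Changing the one word therefore does not settle that second overlap.

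**The case against.** The strongest reply is that the intent can be recovered. Section 5.6.3 says on-treatment, Section 5.3.6 also speaks of the last on-treatment visit, and the Follow-Up row is the exact complement of the *and* reading. The *or* looks like a drafting slip. Section 9 places derivation rules in separate documents, which may already have it right. That is plausible and limits the seriousness, but the SAP text as it stands still gives the wrong rule.

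Several stronger readings are tempting and are not supported:

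- **A count of affected subjects.** A reader might apply the 40% dropout rate in Section 4 to the planned 260 and arrive at 0.40 × 260 = 104. That rate is a planning allowance in the power calculation. The group at issue is subjects who stop drug but stay and keep giving data. The study also ended early, with about 20% having completed Week 52 (Section 3), and the SAP does not give the number actually randomized.
- **Off-drug values certainly enter the tables.** For subjects no longer on drug, Section 3.2 names only height and weight as measurements to be captured. The laboratory shift tables presuppose Follow-Up values, but neither their timing in early stoppers nor their number is given. The visit schedule is in the protocol, which is not shown.
- **BMI is moved out of Week 52.** A Day 364 BMI qualifies for Week 52 as written. Appearing in a Follow-Up summary as well would not change the Week 52 summary.
- **EOT must not coincide with a scheduled week.** EOT is a derived last record, and such coincidence is normal.
- **All safety week windows should be on-treatment only.** Nothing in the SAP requires this.

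No hypothesis test is planned for safety (Section 5.6), and efficacy is descriptive only, so no inferential conclusion turns on the point.

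**Conclusion.** The point holds as an error in a stated rule. Read as written, the EOT row of Table 1 contradicts the Section 5.6.3 definition and overlaps the Follow-Up row that the same section treats as a separate time point. The overlap is |365 − *L*| days: large for early stoppers (281 days for last dose on Day 84, 183 for Day 182) and close to nil for subjects who complete treatment (1 day for last dose on Day 364, none for Day 365, 5 for Day 370).

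The outputs exposed are the laboratory change-to-EOT summaries, the laboratory shift tables and the ECG shift table. The conclusion rests on the literal text and on assumed last-dose days. How many subjects are affected, and whether the tables would look different, cannot be determined from the SAP. The missing precedence between Follow-Up and the scheduled weeks is a lesser, separate ambiguity.

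**What to change.** 1. **EOT row:** define EOT as the last non-missing post-baseline value dated ≤ Day 379 **and** ≤ last dose date + 14 days. Leave the Follow-Up condition as it is, so that the two rows are exact complements. Removing Day 379 from both rows instead would open a gap: with last dose on Day 370, a Day 382 value would be outside Week 52 (337 to 379) and also outside Follow-Up (382 ≤ 384).
2. **Precedence:** add one sentence saying that a record inside a Week 1 to 52 window stays in that window by study day for by-visit summaries, including BMI, height and weight, even when it also meets the Follow-Up condition.
3. **Follow-Up record:** state which single record is used when several qualify, since the row has no target day.

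The cost is a few lines of SAP text and a matching check of the programming specifications. No new data are needed, and the scheduled week windows do not change.

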Change (Absolute Change) from baseline: will be calculated as Post baseline value - Baseline value.

Percent change from baseline: will be calculated and expressed in percentages as $100 \times (\text{Post baseline value} - \text{Baseline value}) / \text{Baseline value}$.

Unscheduled Visits: Unscheduled visit measurements will be included in listings, for derivation of visit windows and computation of baseline/last on-treatment visit.

Outliers: No formal statistical analyses will be performed to detect and/or remedy the presence of statistical outliers.

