5.6.4 Vital Signs

Descriptive statistics for vital signs parameters (e.g., systolic and diastolic BP, pulse, respiratory rate, temperature, weight) and changes from baseline will be presented by visit and treatment group.

Descriptive statistics for vital signs parameters (e.g., systolic and diastolic BP, pulse, respiratory rate, temperature, weight) and changes from baseline will be presented by visit and treatment group.

In addition, clinically notable vital sign values will be identified using the criteria in [Table 2](#). The clinically notable vital sign values will be summarized using frequency count at each visit by treatment group.

Table 2 Vital Sign Criteria

Variable	Criterion value ^a	Change relative to baseline ^a	Clinically notable range
Pulse rate	>120 bpm	Increase of 15 bpm	H
	<50 bpm	Decrease of ≥ 15 bpm	L
Systolic BP	>180 mmHg	Increase of ≥ 20 mmHg	H
	<90 mmHg	Decrease of ≥ 20 mmHg	L
Diastolic BP	>105 mmHg	Increase of ≥ 15 mmHg	H
	<50 mmHg	Decrease of ≥ 15 mmHg	L
Weight	--	Increase of $\geq 7\%$	H
	--	Decrease of $\geq 7\%$	L
Respiratory Rate	>20 bpm	--	H
	< 10 bpm	--	L

BP = blood pressure, H = high, L = low.

- a. Clinically notable means that a value must meet the criterion value and must attain the specified magnitude of change relative to baseline.

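### Clinically notable vital signs are counted only by visit, from one reading per window, so displaced notable readings are missed and no count of subjects ever notable is produced

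*SAP*

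**What the plan says.** SAP 8.1.1 sets the selection rule. Its scope is broad: "Table 1 will be applied to all measurements including those from unscheduled visits and early termination visits to attain the measurement for analysis" for each scheduled visit. The table is headed "Windowing Rules for Safety Endpoints", so vital signs are covered. Where a window holds more than one assessment, "the assessment closest to the target visit day will be used in data analyses"; and "in the event of two assessments being equally close to the scheduled visit day, the latest assessment in the sequence will be used".

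SAP 5.6.4 defines the output. Table 2 gives thresholds, and its footnote says: "Clinically notable means that a value must meet the criterion value and must attain the specified magnitude of change relative to baseline". The only summary of these values is by visit: "The clinically notable vital sign values will be summarized using frequency count at each visit by treatment group".

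SAP 5.3.6 lists what unscheduled readings are for: "Unscheduled visit measurements will be included in listings, for derivation of visit windows and computation of baseline/last on-treatment visit". It names no threshold or worst-value use.

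Other safety data are treated differently. SAP 5.6.3 includes laboratory shift tables to the highest and to the lowest on-treatment value, and SAP 5.6.5 tabulates the maximum post-baseline QTc. Vital signs have thresholds but no summary over the whole treatment period.

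**The concern.** Picking one reading per window is reasonable for by-visit means, where each subject should contribute once. A threshold count asks something else: did this subject have a qualifying value? If the qualifying reading is not the one selected, the by-visit count does not record it.

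A second gap exists even when no reading is displaced. By-visit counts cannot be added up to subjects ever affected. One subject notable at two visits, and two subjects each notable at one visit, give the same row of counts. The natural safety summary, the number and percentage of subjects per arm with any notable value, cannot be recovered from the planned table.

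Section 3 of the SAP says that most planned efficacy tables will not be produced, so the safety tables carry much of the report.

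**Working it through.** The plan states no figure on this point, so there is none to reproduce. The check applies the 8.1.1 rule to readings and compares the result with Table 2 of 5.6.4.

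**Window widths** (8.1.1, Table 1; last day − first day + 1):

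- Week 12: 112 − 71 + 1 = 42 days
- Week 20: 168 − 113 + 1 = 56 days
- Week 28: 224 − 169 + 1 = 56 days
- Week 36: 280 − 225 + 1 = 56 days
- Week 44: 336 − 281 + 1 = 56 days

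**Example in the Week 20 window** (target Day 140; readings are illustrative). Baseline pulse 72 bpm, scheduled Day 140 pulse 68, unscheduled Day 150 pulse 45.

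- Table 2, low pulse: 45 < 50, and the fall is 72 − 45 = 27, against the required 15. The Day 150 value is notable.
- Distances: |150 − 140| = 10 and |140 − 140| = 0. The Day 140 value is kept, and 68 is not notable.
- Result: the subject is not counted at Week 20. If there is a later on-treatment reading, Day 150 is not the EOT value either.

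**Examples in the Week 12 window** (target Day 84). Systolic BP 185 mmHg exceeds 180, and it meets the required rise of 20 if baseline is at most 185 − 20 = 165.

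| Readings | Distances (days) | Kept | Notable value |
|---|---|---|---|
| Day 84: 118; Day 100: 185 | 0; 16 | 118 | lost |
| Day 84: 185; same-day repeat: 118 | 0; 0 (tie, later kept) | 118 | lost |
| Day 80: 185; Day 88: 118 | 4; 4 (tie, later kept) | 118 | lost |
| Day 84: 185; Day 91: 118 | 0; 7 | 185 | kept |

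**How readily displacement occurs.** The rule was run on pairs of days in all nine windows from Week 1 to Week 52. The tolerance of the scheduled visit around its target day is an assumption.

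| Scheduled visit | Abnormal unscheduled reading on another day of the window, displaced by a normal scheduled one | Abnormal scheduled reading displaced by a normal repeat 0–7 days later |
|---|---|---|
| exactly on target | 100% | 12.5% |
| within ±3 days | 93% | 34% |
| within ±7 days | 83% | 45% |

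These are shares of equally weighted day pairs, not predicted event rates. The 12.5% is the same-day repeat alone: 1 of the 8 possible gaps (0 to 7 days).

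**Direction.** The selected readings are a subset of all readings. A subject with a notable value among the selected readings also has one among all readings, and the converse need not hold. So the number notable under the one-value rule is at most the number notable using all readings, both within a window and over treatment.

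**The case against.** The strongest reply is that the rule does not look at the result. It keeps an abnormal scheduled value whenever that value is closer to target, as in the last Week 12 example, and it can let an abnormal repeat replace a normal reading. This stands. A reader might infer that the plan systematically prefers normal repeats, and the document does not support that. It does not rescue the count, because keeping one qualifying value does not make up for dropping another.

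Nor are displaced values always uncounted. Table 1 has an EOT row, and 5.3.6 lets unscheduled readings define the last on-treatment visit, so a displaced reading that is also the last on treatment can reappear there if the table shows EOT. With only about 20% of subjects having completed Week 52 (Section 3), that will not be rare. The values also remain in the listings. Both points stand and limit the loss, but a listing does not give an incidence by arm.

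A reader might also infer that the maximum QTc and the laboratory extremes are affected. The text does not support this: 5.6.3 and 5.6.5 define these over treatment, and 8.1.1 ties windowing to the given scheduled visit. What remains is that 5.3.6 does not say that unscheduled readings feed them. The ECG interpretation shift to end of treatment is a separate design choice and has nothing to do with the windowing rule.

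Finally, safety is descriptive with no hypothesis testing (5.6), so no formal conclusion depends on these counts. The SAP leaves derivation rules and table shells to separate documents (Sections 9 and 11), which might add the missing row. As written, the SAP does not call for it.

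**Conclusion.** The point holds for clinically notable vital signs. Sections 8.1.1 and 5.6.4 together leave a displaced notable reading out of the by-visit counts unless it is also the EOT value, and no per-arm number of subjects ever notable is planned. The direction is certain: unchanged or too low.

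The size, and any difference between arms, cannot be determined, because the SAP does not say how often repeat or unscheduled readings occur. Nor does it say why they are taken, so a reader should not infer a large bias from an assumption that they follow symptoms. The conclusion assumes that 8.1.1 governs the by-visit vital-sign table, which its scope and its title both indicate. This is a change that should be made to the safety reporting; it does not call the study's data into question.

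**What to change.** - **5.6.4:** add, for each Table 2 criterion, the number (%) of subjects per arm with at least one clinically notable value at any time on treatment, using all scheduled and unscheduled post-baseline on-treatment readings. Keep the by-visit counts if wanted.
- **8.1.1:** state that the closest-to-target rule and its tie rule apply to by-visit summaries only.
- **5.3.6 (clarification only):** add to the unscheduled-visit sentence that these readings also feed the maximum QTc and the highest and lowest laboratory summaries.

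The cost is SAP wording and one extra table row per criterion. The data are already collected. Reported counts of notable values may rise slightly.
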